- Any clinically significant abnormal laboratory findings or other abnormal safety assessments which are associated with the underlying disease, unless judged by the investigator to be more severe than expected for the participant's condition.
- The disease/disorder being studied or expected progression, signs, or symptoms of the disease/disorder being studied, unless more severe than expected for the participant's condition.
- Medical or surgical procedure (eg, endoscopy, appendectomy): the condition that leads to the procedure is the AE.
- Situations in which an untoward medical occurrence did not occur (social and/or convenience admission to a hospital).
- Anticipated day-to-day fluctuations of preexisting disease(s) or condition(s) present or detected at the start of the study that do not worsen.
- Worsening of signs and symptoms of the malignancy under study should be recorded as AEs in the appropriate section of the CRF. Disease progression assessed by measurement of malignant lesions on radiographs or other methods should not be reported as AEs.

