- Examples of such events include invasive or malignant cancers, intensive treatment in an emergency room or at home for allergic bronchospasm, blood dyscrasias or convulsions that do not result in hospitalization, or development of drug dependency or drug abuse.
- Progression of the malignancy under study (including signs and symptoms of progression) should not be reported as an SAE unless the outcome is fatal within the active collection period. Hospitalization due to signs and symptoms of disease progression should not be reported as an SAE. If the malignancy has a fatal outcome during the study or within the active collection period, then the event leading to death must be recorded as an AE on the CRF, and as an SAE with CTCAE Grade 5 (see the Assessment of Intensity section).

• Suspected transmission via a Pfizer product of an infectious agent, pathogenic or non-pathogenic, is considered serious. The event may be suspected from clinical symptoms or laboratory findings indicating an infection in a patient exposed to a Pfizer product. The terms "suspected transmission" and "transmission" are considered synonymous. These cases are considered unexpected and handled as serious expedited cases by pharmacovigilance personnel. Such cases are also considered for reporting as product defects, if appropriate.

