# 6.7.1.2. Other Adverse Events of Clinical Interest

Other adverse events of clinical interests (oAECIs) include the following events:

- Infections:
  - The MedDRA SOC of Infections and infestations.
- Cytopenias:
  - The MedDRA PTs for cytopenias are defined in Appendix 2.
- Hypogammaglobulinemia:
  - Including the MedDRA PTs: Blood immunoglobulin G decreased, Hypogammaglobulinaemia, Hypoglobulinaemia, Immunoglobulins decreased and Globulins decreased.
- Injection site reactions:
  - The MedDRA HLT of Injection site reactions.
- Secondary malignancies:
  - The MedDRA SOC of Neoplasms Benign, Malignant and Unspecified.

All the analyses will be performed by each individual oAECI separately. For cytopenias, the individual PTs (ie, not clustered terms) will be reported in the summary.

A high-level summary of each of oAECI will be provided including the following, if applicable:

- Any oAECIs;
- Serious oAECIs;
- oAECIs by maximum toxicity grade;
- oAECIs leading to dose interruptions;
- oAECIs leading to dose reductions;
- oAECIs leading to dose interruptions or reductions;
- oAECIs leading to permanent discontinuation of study intervention.

The following summary will be provided for each oAECI, if applicable:

- oAECI by PT and maximum severity grade (all causality and treatment-related);
- Time to onset of the oAECI, time to resolution, and duration of the oAECI with descriptive statistics as well as broken down in categories.

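### The secondary-malignancy category is the whole neoplasm SOC, so it counts benign tumours and can count fatal study myeloma

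*SAP*

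**What the plan says.** SAP 6.7.1.2 names five categories of other adverse events of clinical interest. One is headed "Secondary malignancies", and its full definition is "The MedDRA SOC of Neoplasms Benign, Malignant and Unspecified". There is no restriction to malignant terms, no exclusion of myeloma or plasmacytoma terms, and no review step.

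For each category the same section plans, where applicable:
- a high-level table (any, serious, by maximum grade, and leading to interruption, reduction or discontinuation);
- a table by PT and maximum grade;
- summaries of time to onset, time to resolution and duration.

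SAP 6.7.1 bases AE analyses on treatment-emergent events. SAP 3.5 sets the window from first dose to 90 days after last dose, or to the day before new anticancer therapy if that is sooner.

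On the study disease, Protocol 10.3.2 says that progression "should not be reported as an SAE unless the outcome is fatal within the active collection period". In the fatal case, "the event leading to death must be recorded as an AE on the CRF, and as an SAE with CTCAE Grade 5". Protocol 10.3.1 adds "Worsening of signs and symptoms of the malignancy under study should be recorded as AEs in the appropriate section of the CRF", but also "Disease progression assessed by measurement of malignant lesions on radiographs or other methods should not be reported as AEs".

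**The concern.** The label and the search definition describe different things. A reader takes a secondary-malignancy row to mean new cancers other than the one being treated. The definition instead retrieves everything coded to a neoplasm SOC, in a trial where every participant has a neoplasm at entry.

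Two kinds of event can be wrongly included. Benign and unspecified tumours qualify by the SOC's own name. The study myeloma qualifies whenever an AE is coded to a neoplasm term for it. A fatal case entering this way would appear as a Grade 5 event under a secondary-malignancy heading. SAP 6.7.2 separately tabulates the primary reason for death from the death and survival follow-up CRFs, so the same participant could be a myeloma death in one table and a fatal secondary malignancy in another.

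What is at stake is how a descriptive safety summary reads: its headline rate, its grade distribution and its timing summaries.

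**Working it through.** The plan states no figure for this category, so there is nothing to reproduce. The check sets the definition against the recording rules and then shows the scale per participant.

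**Step 1: benign and unspecified tumours.** The SOC name in SAP 6.7.1.2 includes both, and nothing in the section removes them. This inclusion needs no assumption about how the study disease is coded.

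**Step 2: can the study myeloma become an AE?** Protocol 10.3.1 keeps the studied disease and its expected progression out of the AE definition unless more severe than expected, and keeps out progression found by measurement. Protocol 10.3.2 then makes an exception for a fatal outcome in the active collection period: an AE and a Grade 5 SAE must be recorded. The fatal rule is therefore the main route, and unexpectedly severe disease is a smaller one.

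**Step 3: can that AE be treatment-emergent?** Protocol 8.3.1 collects AEs for at least 90 days after last dose. SAP 3.5 counts events starting up to 90 days after last dose, cut at new anticancer therapy. The two periods largely overlap, so a Grade 5 myeloma AE can enter the tables. Events starting after new therapy, or later than 90 days, do not.

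**Step 4: would it fall in the SOC?** Only if the reported term is coded to a neoplasm. Neither document fixes that term. A death reported as myeloma would qualify; one reported as a complication or under a general progression term might not.

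**Step 5: does anything downstream correct it?** The by-PT table shows which terms are benign or myeloma. The any, serious and maximum-grade rows still count them, as do the time-to-onset and duration summaries.

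**Step 6: how are the neighbouring categories defined?** The SAP uses a PT list for cytopenias (Appendix 2), named PTs for hypogammaglobulinemia (6.7.1.2), a neuropathy query with Guillain-Barre terms removed (6.7.1.1), and clinical review of immune-related neurologic events (7.1.2). None of these devices is applied to neoplasms.

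**Step 7: scale.** The denominators are the treated participants in Protocol 9.2: 123 in Cohort A and 64 in Cohort B, so 123 + 64 = 187 combined. Each misclassified participant adds 1/N:
- Cohort A: 1/123 = 0.8 percentage points.
- Cohort B: 1/64 = 1.6 percentage points.
- Combined: 1/187 = 0.5 percentage points.

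The number misclassified is not in the documents. As an assumption only, with k participants misclassified of 187:
- k = 5: 5/187 = 2.7 percentage points.
- k = 10: 10/187 = 5.3 percentage points.
- k = 20: 20/187 = 10.7 percentage points.

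**The case against.** The strongest reply is that the harm from fatal myeloma depends on coding that nobody can see in these documents. The protocol requires the event leading to death to be recorded, not that it be called myeloma. That stands, and it is why the conclusion says the category can count the study disease. It does not touch the benign and unspecified tumours.

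A second reply is that Protocol 10.3.1 mostly narrows the route. Signs and symptoms are not themselves the neoplasm, and measured progression is kept out of AE reporting. This also stands; it leaves fatal disease as the main entry point. Likewise, Protocol 7.1 lists progression as its own reason for stopping treatment, so the row for discontinuation need not be much affected.

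A third reply is that the by-PT table and the cause-of-death outputs let a careful reader recount. They do, but the headline rows and timing summaries stay uncorrected, and these are the figures most likely to be carried forward.

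A fourth is that whole-SOC retrieval is also used for infections in the same list. There, however, the label matches the SOC. Here it claims something narrower.

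A reader might go further and infer that fatal secondary malignancies in this trial will mainly be disease progression, or that the true count will be exceeded several times over. The documents support neither inference: they give no number of myeloma AEs, benign tumours or second cancers. Nor do they describe this category as an outcome intended for labelling.

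**Conclusion.** The definition does not fit its label and should be narrowed. Inclusion of benign and unspecified neoplasms follows directly from the text. Inclusion of study myeloma is possible rather than certain: it needs an AE coded to a neoplasm term and starting within the on-treatment window, and the fatal-outcome rule in Protocol 10.3.2 is the likeliest source. The any, serious and maximum-grade rows and the timing summaries can then overstate secondary malignancies, by the per-participant amounts shown above; the total is unknown.

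The reach is limited. This is a descriptive summary of an event category outside the AESI list. The primary endpoint, the error rates and the enrolment-hold rules do not use it. The change is worth making because the error is plain and the correction is cheap, not because any trial conclusion depends on it.

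**What to change.** In SAP 6.7.1.2, replace the SOC with a definition that:
- takes malignant-neoplasm terms only, through a PT list or a standardized query limited to malignant terms;
- excludes terms for the myeloma or plasmacytoma under study and for its progression;
- requires a documented medical review of the resulting PT list before database lock, so that ambiguous terms are settled before the tables are final.

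Fatal myeloma would still be reported in the general AE tables and the deaths table, so no information is lost. The cost is a revised SAP entry and a small amount of medical review time. No new data are collected.

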#### 6.7.2. Deaths

The frequency (number and percentage) of participants in the Safety Analysis Set who died at any time, who died within 28 days of the first dose of study intervention, and who died within 90 days after last dose of study intervention as well as the primary reason for death, will be tabulated based on information from the 'Death Details' and 'Survival Follow-Up' CRFs.

Date and cause of death will be provided in individual participant data listing together with selected dosing information (date of first/last administration, dose).

In addition, deaths due to COVID-19 may be presented in a separate listing if there is significant impact of COVID-19.

#### 6.7.3. Laboratory Data

Laboratory results will be converted to International System of Units (Système International d'unités, SI) units which will be used for applying severity grades and for all summaries.

As described in Section 3.4, baseline will be defined as the last assessment performed on or prior to date of the first dose of study intervention. If there are multiple assessments that meet the baseline definition on the same day without the ability to determine which was truly last, then the worst grade will be assigned as the baseline grade.

Results collected as strict inequalities (eg, >10, <10) will be converted to numeric values adding or subtracting a factor of 0.001. Expressions of the form " $\geq$ " or " $\leq$ " will be converted to the end point. These numeric values will be evaluated for clinically significant abnormalities, but will not be included in calculations of summary statistics except for efficacy related laboratory results. Additional data handling rules for efficacy related laboratory data will be described in the programming plan.

Additionally, laboratory results will be programmatically classified according to NCI-CTCAE version 5.0 grade as appropriate. Non-numerical qualifiers will not be taken into consideration in the derivation of grade (eg, hypokalemia Grade 1 and Grade 2 are only distinguished by a non-numerical qualifier and therefore Grade 2 will not be derived). In summary statistics the number and percentage of participants corresponding to grades that only include non-quantitative criteria will be displayed as a blank or NA (not assessed) rather than 0. If there is any overlap between grade criteria (eg, CTCAE grading criteria for Creatinine Increased - a value can fall into one range based on comparison to ULN and another range based on comparison to baseline), the highest (worst) grade would be assigned to that record. Grade 5 is defined in the CTCAE criteria guidance as an event with an outcome of death. Since laboratory data does not collect an outcome, Grade 5 is not used when programmatically grading laboratory data. For laboratory tests without CTCAE grade definitions, results will be categorized as normal, abnormal, or not done.

Grade 0 or Outside Toxicity Reference (OTR) is not defined specifically in the CTCAE guidance. However, programmatically this is used as a category to represent those participants who did not meet any of the Grades 1 to 4 criteria. If the laboratory value is evaluable for CTCAE criteria grading (numeric value is present, valid units and ranges are present as required to allow conversion to standard units and grading), and does not qualify for any of the Grade 1-4 criteria for a given lab test, then the value is assigned as Grade 0 or OTR.

Several of the CTCAE terms (including Hypo/Hypercalcemia, Chronic Kidney Disease, and Activated Partial Thromboplastin) can be derived using several laboratory tests (analytes) as follows:

- Hypo/Hypercalcemia graded by Serum Calcium or Ionized Calcium;
- Chronic Kidney Disease graded by estimated Glomerular Filtration Rate (eGFR) or Creatinine Clearance;
- Activated Partial Thromboplastin Time Prolonged (aPTT) graded by Partial Thromboplastin Time (PTT) or activated Partial Thromboplastin Time (aPTT).

For WBC differential counts (total neutrophil [including bands], lymphocyte, monocyte, eosinophil, and basophil counts), the absolute value will be used when reported by the lab and will be graded following the CTCAE guidance.

When only percentages are available (this is mainly applicable for neutrophils and lymphocytes, because the CTCAE grading is based on the absolute counts), the absolute value is derived as follows:

Derived differential absolute count = (WBC count) × (Differential %value / 100)

If the investigator reports both the absolute and % value for Neutrophils or Lymphocytes from the same laboratory sample date and participant, ONLY the absolute value will be graded. The % value will not be graded in this scenario.

If the % value is converted to the differential absolute count for grading and the LLN for the differential absolute count is not available (only LLN for % is available) then Grade 1 will be assigned if the following conditions are met:

- Lymphocyte count decreased:
  - derived absolute count does not meet Grade 2-4 criteria, and
  - % value < % LLN value, and
  - derived absolute count  $\geq 800/\text{mm}^3$ .
- Neutrophil count decreased:
  - derived absolute count does not meet Grade 2-4 criteria, and
  - % value < % LLN value, and
  - derived absolute count  $\geq 1500/\text{mm}^3$ .

For calcium, CTCAE grading is based on Corrected Calcium and Ionized Calcium. Corrected Calcium is calculated from Albumin and Calcium as follows:

Corrected Calcium (mg/dL) = measured total calcium (mg/dL) – 0.8 [serum albumin (g/dL)-4]

Creatinine clearance is calculated as follows:

- Male: Creatinine Clearance = ((140 Age) / (Serum Creatinine)) \* (Weight / 0.814);
- Female: Creatinine Clearance (eGFR) = 0.85\* ((140 Age) / (Serum Creatinine)) \* (Weight / 0.814);

Note: the SI unit of Serum Creatinine is "micromol/L", the unit of weight is "Kg".

Abnormalities will be described using the worst grade overall. Worst case overall will be determined using laboratory results from scheduled and unscheduled visits. Several laboratory tests have bi-directional grading criteria defined so that both low (hypo) and high

(hyper) values can be graded separately. Each criterion will be summarized separately. In the cases where a value is graded as a Grade 1, 2, 3, or 4 for one of the directions, that value will also be assigned as a Grade 0 for the opposite direction for that test. For example, a value meeting the criteria for Grade 3 Hypercalcemia will be classified as a Grade 0 Hypocalcemia. For CTCAE terms that can be derived using one of several laboratory tests, the maximum postbaseline grade for a given participant and CTCAE term will be the maximum across all possible laboratory tests.

Additional laboratory results that are not part of CTCAE will be presented according to the following categories by scheduled timepoint as well as overall: below normal limit, within normal limits, and above normal limits. In the unlikely event that for a given participant, clinically significant abnormalities are noted in both directions (eg, > Upper Limit of Normal (ULN) and < Lower Limit of Normal [LLN]), then both abnormalities are counted.

The following summary tables will be created:

- Shift summary of laboratory parameters during the on-treatment period by maximum CTCAE grade;
- Shift summary of laboratory parameters from ≤ Grade 2 at baseline to ≥ Grade 3 postbaseline;
- Shift summary of laboratory test results with no CTCAE criteria by worst on treatment assessment.

All laboratory test results will be presented in a data listing sorted by participant identifier, laboratory test, and date/time of collection. The CTCAE grades and the classifications relative to the laboratory reference ranges will be presented. Values outside laboratory normal ranges will be flagged where appropriate.

**Liver function tests:** Alanine aminotransferase (ALT), aspartate aminotransferase (AST), Alkaline Phosphatase (ALP), and total bilirubin (TBILI) are used to assess possible drug induced liver toxicity. The ratios of test results over the ULN will be calculated and classified for these 3 parameters during the on-treatment period.

Summary of liver function tests will include the following categories. The number and percentage of participants with each of the following during the on-treatment period will be summarized:

- ALT≥3×ULN, ALT≥5xULN, ALT≥10×ULN, ALT≥20×ULN;
- AST≥3×ULN, AST≥5xULN, AST≥10×ULN, AST≥20×ULN;
- (ALT or AST)≥3×ULN, (ALT or AST)≥5×ULN, (ALT or AST)≥10×ULN, (ALT or AST)≥20×ULN;
- TBILI≥2×ULN;

- Concurrent ALT≥3×ULN and TBILI≥2×ULN;
- ALT≥3×ULN and TBILI≥2×ULN at any timepoint;
- Concurrent AST≥3×ULN and TBILI≥2×ULN;
- AST≥3×ULN and TBILI≥2×ULN at any timepoint;
- Concurrent (ALT or AST)≥3×ULN and TBILI≥2×ULN;
- (ALT or AST)  $\geq$  3×ULN and TBILI  $\geq$  2×ULN at any timepoint;
- Concurrent (ALT or AST) >3×ULN and TBILI >2×ULN and ALP >2×ULN;
- (ALT or AST) >3×ULN and TBILI >2×ULN and ALP >2×ULN at any timepoint;
- Concurrent (ALT or AST) >3×ULN and TBILI >2×ULN and ALP <2×ULN or missing;
- (ALT or AST)≥3×ULN and TBILI≥2×ULN and ALP≤2×ULN or missing at any timepoint.

Concurrent measurements are those occurring on the same date.

Categories will be cumulative, ie, a participant with an elevation of AST $\geq$ 10×ULN will also appear in the categories  $\geq$ 5×ULN and  $\geq$ 3×ULN. Liver function elevation and possible Hy's Law cases will be summarized using frequency counts and percentages.

An evaluation of Drug-Induced Serious Hepatotoxicity (eDISH) plot will also be created, with different symbols for different cohorts, by graphically displaying:

- Peak serum ALT(/ULN) vs peak total bilirubin (/ULN) including reference lines at ALT=3×ULN and total bilirubin=2×ULN;
- Peak serum AST(/ULN) vs peak total bilirubin (/ULN) including reference lines at AST=3×ULN and total bilirubin=2×ULN.

In addition, the following listings of all TBILI, ALT, AST and ALP values will be provided:

- For participants with a postbaseline TBILI≥2×ULN, ALT≥3×ULN or AST≥3×ULN and ALP≤2×ULN or missing at any timepoint;
- For participants with a postbaseline TBILI≥2×ULN, ALT≥3×ULN or AST≥3×ULN and ALP≤2×ULN or missing at the same visit.

# 6.7.4. Vital Signs

Vital sign data will be listed.

# 6.7.5. Electrocardiograms

Triplicate ECGs are required at each assessment. ECG assessments reported by the site will include PR, HR, QT, QRS, and QTcF. A mean score is calculated and reported for any replicate measurements having the same nominal visit. All summary statistics, analyses and figures will be based on the triplicate averaged data. Any data obtained from ECGs repeated for safety reasons after the nominal time-points will not be averaged along with the preceding triplicates.

ECG summaries will include all ECG assessments from the on-treatment period. RR will be derived from HR. QTcF will be programmatically derived from QT and HR using the following formula:

$$QTcF(msec) = QT(msec)/\sqrt[3]{RR(sec)}$$

All ECG assessments will be listed, and those collected outside the on-treatment period will be flagged in the listing.

QTcF will be summarized by maximum on-treatment values using the following categories:

- <450 msec;
- $\geq$ 450 msec but  $\leq$ 480 msec;
- >480 msec but  $\leq$ 500 msec;
- >500 msec.

Unscheduled assessments will be utilized in addition to planned assessments. Shift tables will be provided for baseline QTcF value versus worst on-treatment value. Additionally, maximum increases from baseline (including scheduled and unscheduled assessments) will be summarized based on the following categories:

- Change >60 msec;
- Change >30 msec but  $\le 60$  msec;
- Change  $\leq 30$  msec.

Data listings will contain the means from a triplicate as well as the parameters from each of the 3 ECGs. Note that using the mean value may result in a participant having a measurement that is not represented by an actual ECG.

# 6.7.6. Neurological Examinations

A shift summary of baseline status by worst status postbaseline will be presented for each subcategory. Shift summaries over time may also be generated.

